#### Data Security

A tertiary risk might include unintentional disclosure of confidential test information, but confidentiality will be strictly maintained in data storage, manipulation, and presentation.

This study will collect PHI (i.e., data, in any format, which requires protection due to the risk of harm that could result from inadvertent or deliberate disclosure, alteration or destruction) from all participating subjects. PHI used in this study will include individually identifiable medical and health data and personal information, such as age, educational level, gender and ethnicity. Subjects' medical diagnoses will be used for the purpose of enrollment and personal information, such as age, gender, and education, will be used to characterize the subject pool utilized in this study. Addresses and telephone numbers will also be collected as a means to contact the subjects for follow-up when indicated. Participant identity will be coded immediately upon entry into the study, and neither the participants' names nor any identifying information will be present in the data set. The computerized system where data will be stored will not leave the protected VA environment unless the data storage components are removed or destroyed. Data collected in other areas (testing rooms) will be brought to the lab and locked away each night. Only approved study personnel will have access to this information.

Presentation of the results will involve group data and the subjects' identity will not be disclosed. In the event of a real or suspected breach of security, the VA Police, Information Security Officer, and the Privacy Officer will be notified. Overall, the proposed study poses no significant increase in risk than what would normally be present in proper clinical management of and frequently prescribed psychological treatment and medical procedures (e.g., UPDRS motor exam) for PD patients.

Adverse Events (AE) and Serious Adverse Events (SAE), as defined below, will be monitored throughout the study duration.

An Adverse Event (AE) is any untoward physical or psychological occurrence in a human subject participating in research. A related AE, death, or problem is an AE, death, or problem that may reasonably be regarded as caused by, or probably caused by, the research.

A Serious Adverse Event (SAE) is an untoward occurrence in human research that results in death, a life-threatening experience, inpatient hospitalization, prolongation of hospitalization, persistent or significant disability or incapacity, congenital anomaly, or birth defect, or that requires medical, surgical, behavioral, social, or other intervention to prevent such an outcome.

SAEs are not anticipated as the interventions and tests that will be used are often prescribed in the standard clinical management of patients (i.e., neuropsychological testing, behavioral interventions). Potential AEs include the (1) need to break confidentiality, (2) loss of data for any reason, and (3) inadvertent harm caused by participation in the study. Suicidality in PD patients is typically a rare occurrence, however, patient suicidality will be assessed and monitored throughout the duration of the study. If the need to break confidentiality arises or data is lost the participant and VA IRB will be notified immediately.

AEs and SAEs will be documented and reported to VA IRB, and clinically managed as appropriate, including participant hospitalization if necessary. For each event that occurs, we will create a report that includes the date of the occurrence, description of the event, how it was reported and to whom, as well as any other pertinent information (i.e. medical related information of the incident).

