Given the age and medical condition (i.e., Parkinson's disease) of the participants, it is possible that individuals may experience medical or psychological changes unrelated to the study that would necessitate early termination of the study. If the individual situation warrants, participants may be able to rejoin a later group. Because both interventions (Psychoeducation/Supportive Care and MBSR) are not group therapy, there is no requirement that individuals will share personal and/or mental-health information. However, should any information be conveyed that causes study staff to be concerned about that participant's psychological well-being, appropriate referrals to the VA Geropsychiatry Clinic may be provided to veterans, or other appropriate community resources for veterans and non-veterans will be provided.

Due to the fall risk associated with individuals with PD, we will use the baseline MDS-UPDRS falling item (#13) in which a history of falls is categorized on a Likert scale from 0 (none) to 4 (falls >once per day). A history of falls as assessed by the MDS-UPDRS appears to be one of the best predictive methods of subsequent falls at this time. Those individuals who endorse a history of falling or score >0 on the MDS-UPDRS falling item, will be closely monitored. Should an individual who is at risk for falling be identified, we will offer assistance during each class to escort the individual to and from the intervention room, from their vehicle, as well as to and from the bathroom, if needed. As standard in MBSR, all participants will be encouraged to work within their own personal limits and preferences. Alternatives to the standard exercises will be offered. These alternatives include sitting in a chair in lieu of floor exercises; lying down for standing exercises; omitting certain (e.g., walking) meditations; and/or visualizing the movements in lieu of acting them out. These options are standard in MBSR and have also been implemented in other trials of MBSR for PD.

Suicidal ideation (SI) will be assessed by Beck Depression Inventory (BDI-II) item #9 at each assessment (i.e., pre-, post-, 6- and 12-months). Should an individual indicate  $\geq 1$  on the BDI-II item 9, the tester will immediately notify a licensed clinician on the protocol. The clinician will

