conduct a thorough clinical evaluation of SI to determine appropriateness to continue in the study and provide any necessary referrals. In addition, each week during the intervention, the participants will complete a brief form which will contain two questions regarding changes in mood and medications. Should a participant indicate mood changes, mood and SI will be evaluated by a licensed clinician to determine appropriateness to continue in the study.

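### The adverse-event examples do not match the adverse-event definition, and no question on injuries, later falls or hospital stays is described, so physical harms may be incompletely captured

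*Combined protocol and SAP*

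**What the plan says.** All the safety-reporting text is in Section 15, mostly under Data Security.

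- **AE definition.** "An Adverse Event (AE) is any untoward physical or psychological occurrence in a human subject participating in research". A related event is defined separately, as one that the research caused or probably caused. AEs and SAEs are to be monitored for the whole study.
- **SAE definition.** "A Serious Adverse Event (SAE) is an untoward occurrence in human research that results in death, a life-threatening experience, inpatient hospitalization, prolongation of hospitalization", followed by further outcomes. It carries no condition on cause.
- **Examples of AEs.** "Potential AEs include the (1) need to break confidentiality, (2) loss of data for any reason, and (3) inadvertent harm caused by participation".
- **Expectation.** "SAEs are not anticipated as the interventions and tests that will be used are often prescribed" in routine care. Earlier in Section 15, however, age and Parkinson's disease are given as reasons why "it is possible that individuals may experience medical or psychological changes unrelated to the study".
- **Scheduled questions.** Each week during the intervention participants fill in "a brief form which will contain two questions regarding changes in mood and medications". BDI-II item 9 is asked at all four assessments. The MDS-UPDRS falling item is used at baseline to identify people at risk of falls, who are then to be monitored closely.
- **Reporting.** AEs and SAEs go to the IRB, with a report for each one.

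The form's prompt for Section 15 asks, where applicable, for the frequency of safety data collection and of cumulative review. For AEs and SAEs the answer gives neither.

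**The concern.** There are two linked problems. First, someone coding events from the examples would enter lost data as an AE. The only clinical example is harm that participation caused, so it gives no prompt to record a fall or an admission judged unrelated. Second, the commitment to monitor throughout has no described means of asking about physical events. The protocol itself recognises a fall risk and offers alternatives to standing, floor and walking exercises, yet the falls item is described at baseline only.

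At stake is how the safety counts can be read. If physical events are recorded only when someone volunteers them, a low count may reflect the way events were collected rather than their absence. If data incidents are in the same count, the total is not a count of harms.

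**Working it through.** The plan gives no figure for event rates or capture, so there is nothing to reproduce. The check is mainly a comparison of text, with some arithmetic for scale.

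**Step 1: examples against the definition.**

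| Example in Section 15 | Physical or psychological occurrence in a participant? |
|---|---|
| Having to break confidentiality | Not in itself; it may accompany one (for example suicidality) |
| Loss of data | No |
| Harm caused by participation | Yes, but only the related subset |

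No example is an unrelated clinical event, although the definition covers such events.

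**Step 2: scheduled items described.**

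| Item | When | Covers injury, fall or hospital stay? |
|---|---|---|
| Health history questionnaire (Section 9) | At consent, for eligibility | Before the intervention only |
| MDS-UPDRS falling item (Section 15) | Baseline | Past falls only |
| Weekly form (Sections 9 and 15) | During the 8 weeks | No: mood and medications |
| BDI-II item 9 (Section 15) | Baseline, 8 weeks, 6 and 12 months | No: suicidal ideation |
| UPDRS Part III and Hoehn and Yahr (Section 9) | Baseline and 12 months | Described as motor function and severity |
| Reminder calls (Section 9) | 2 months and 1 month before each testing session | Described for retention only |

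None of the instruments listed in Section 9.8 is named as an adverse-event or health-event form. Section 9 says that the study questionnaires are attached to the submission. They were not available, so the finding is that no such question is described.

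**Step 3: follow-up time after the weekly form ends.** Section 9 can be read with the 12 months running from the end of the intervention or from baseline.

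- From the end of the intervention: 8 + 52 = 60 weeks, and 52/60 = 87% comes after week 8.
- From baseline: 52 − 8 = 44 weeks, and 44/52 = 85% comes after week 8.

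This is a share of time, not of events.

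**Step 4: can the missed share be computed?** No, because it depends on a capture rate that the documents do not give. For illustration, assume a constant event rate, full capture in the first 8 weeks (generous, since the weekly form does not ask about physical events) and a fraction c captured later. On the 60-week clock, overall capture = (8 + 52c)/60:

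- c = 0: 8/60 = 13%
- c = 0.25: 21/60 = 35%
- c = 0.50: 34/60 = 57%
- c = 0.75: 47/60 = 78%

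The range is too wide to support a statement about how much is lost.

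**Step 5: are hospitalizations likely at all?** The documents give no rate. Assume a risk p per participant over follow-up. With 88 participants, the expected number hospitalized is 88p and the chance of at least one is 1 − (1 − p)^88:

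- p = 1%: 0.88 expected, 59%
- p = 2%: 1.76 expected, 83%
- p = 5%: 4.4 expected, 98.9%
- p = 10%: 8.8 expected, over 99.9%

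With 80 participants, the planned number after attrition, the first three chances are 55%, 80% and 98.3%. Under the protocol's own SAE definition, at least one SAE is more likely than not across this assumed range. This shows only that such events are to be expected, not how many would be missed or misclassified.

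**The case against.** A fair defence has several parts.

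- **The definition governs.** The list is introduced as non-exhaustive, the definition has no condition on cause, and a report is required for each event. A reader might infer that the plan restricts AEs to harm caused by participation and so excludes unrelated events. The documents do not support that. The mismatch remains: data loss does not fit the definition.
- **Missed events are an inference.** A reader might conclude that most harms after week 8 will be missed. The documents do not show this. BDI-II item 9 is asked at 8 weeks, 6 and 12 months, mood is measured at those visits, participants at risk of falls are to be monitored closely, and visits and calls give occasions to volunteer events. The attached forms may also contain more. What stands is that no routine question on physical events is described.
- **The SAE sentence removes no duty.** Its stated reason concerns the interventions and tests, so it reads as an expectation about research-caused events. SAEs must still be documented and reported, and Section 15 calls unrelated changes only possible. This is not a contradiction; the sentence needs its scope stated.
- **Confidentiality.** The wording can mean a deliberate disclosure made necessary by a psychological event. That event is then the AE, and the disclosure is a separate problem to report. Security breaches already have their own notification route (Section 15, Data Security, and Section 27.6).
- **Consequences.** The study is described as minimal risk (Section 18), the aims concern quality of life, cognition and mood, and no between-arm comparison of harms is planned. The described items apply to both arms, so it does not follow that the arms could never be compared. Counts in both may still be incomplete.

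**Conclusion.** The point holds as a gap in the described safety collection and an inconsistency in the text. Data loss and having to break confidentiality are listed as AEs although neither is in itself an AE under the stated definition, so counts may mix data incidents with clinical harms. No scheduled question on injuries, falls after baseline or hospital stays is described, and 85% to 87% of follow-up time comes after the weekly form ends. Capture of physical events and hospitalizations may therefore be incomplete and depend on volunteered reports.

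The extent of any under-capture cannot be computed. The conclusion assumes that the attached questionnaires, which were not available, contain no such question; if one does, that half of the point falls away and only the mismatch of examples and definition remains. The primary efficacy analysis is unaffected. The change is a cheap improvement.

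**What to change.** 1. Reconcile the AE definition and the examples in Section 15, so that the definition applies to every event whatever its cause, with relatedness recorded separately.
2. Log data loss and confidentiality incidents as reportable problems, apart from AEs. Where a disclosure accompanies a psychological event, record the event itself as the AE.
3. State that the sentence on SAEs not being anticipated refers to intervention-related SAEs.
4. Add one fixed, identically worded question (injury or fall, hospital stay, other new health problem) to the existing weekly form and to the 8-week, 6-month and 12-month assessments, in both arms. If an attached questionnaire already asks this, cite it in Section 15.
5. Report AE and SAE counts by arm.

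The cost is a text edit and one question at contacts that already take place, with no added visit. The downside is more AE reports to process.

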## Section 17 - Potential Benefits

### 17) Discuss benefits that may be gained by the subject as well as potential benefits to society in general (see ? for guidance)

While there is always the potential that participants will not receive any direct benefit from participating in this study, there is also the probable likelihood, based on our preliminary data and previously published research, that participants will experience improvements in quality of life and/or non-motor symptoms, such as cognition and mood. Even if participation in this study does not provide any direct benefits to the participants, their participation will help advance our knowledge regarding the effects of MBSR in PD.

## Section 18 - Risk/Benefit Analysis

### 18) Discuss why the risks to subjects are reasonable in relation to the anticipated benefits to subjects and in relation to the importance of the knowledge that may reasonably be expected to result.

The primary risks of participating in this study are fatigue, test anxiety, and emotional discomfort. As noted above, there are specific plans in place to lessen the likelihood of any of these potential risks.

To the best of our knowledge, the risk/benefit ratio appears to be reasonable in relation to the anticipated benefits to be gained by the participants and others. The study involves minimal risk and most participants are eager to contribute to furthering Parkinson's disease research.

## Section 20 - Compensation for Participation

### 20) Provide all details and justifications of the compensation plan. See ? for detailed requirements.

Participants will receive a payment of \$75 for each of the four neuropsychological testing sessions they complete (pre- and post-intervention/support and 6- and 12-month follow-ups).

## Section 27 - Privacy, Confidentiality, and Information Security

**27a) Provide a brief description of how participant privacy and confidentiality will be protected in this study. Describe the circumstance under which it may be possible for a research team member to identify subjects and any related protections or assurances to prohibit or avoid identification. Describe how the number of people with access to identifiers for research purposes is limited in order to protect a participant's privacy.**

Participant identity will be coded immediately upon entry into the study, and neither the participants' names nor any identifying information will be present in the data set. Data collected in other areas (testing rooms) will be brought to the lab and locked away each night. Only approved study personnel will have access to this information.

Hard copy PHI is collected and will be stored in a locked filing cabinet in the PI's lab space. All electronic PHI collected will be stored on a VA computer within the secure VA network. PHI will be stored separately from coded data. Only research staff listed on the protocol will have access to the identifiers and data.

In the groups, which are audio recorded, subjects are asked to call each other only by their first name, to help avoid confidentiality breach.

In the event of a real or suspected breach of security, the VA Police, Information Security Officer, and the Privacy Officer will be notified.

**27.b) Entry of a CPRS Research Informed Consent Note is required when subjects will be admitted as inpatients or treated as an outpatients for research and the study involves research medical care or may affect medical care.**

- *If a Research consent Note is required, then a Research Progress Note should also be entered for each procedure or intervention.*

- *Scanning the Consent and HIPAA Authorization into CPRS is not required. Linking the Consent to the Research Informed Consent Note may be permitted and can be useful for trials involving the Research Pharmacy or when research will be performed in conjunction with clinical procedures.*
- *For Non-Veterans, if Research Informed Consent Notes are entered, then the NOPP Acknowledgment must be scanned into the record. Otherwise a copy of the signed NOPP must be retained with the Investigator's research records and a copy sent to the Privacy Officer; see the ? Help for more information.*

27.b1) Is entry of CPRS notes required based on the above criteria?

- CPRS notes are needed for ALL subjects
- CPRS notes are needed for SOME subjects
- CPRS notes are NOT needed for any subjects

Identify for which group or groups CPRS records will be entered and to which groups this requirement does not apply.

CPRS will be entered for subjects who pass eligibility screening, are enrolled, and attend at least one group session. CPRS records will not be entered for those who fail eligibility screening after signing informed consent or who drop out prior to groups.

### 27c) Select the VA Sensitive Information (VASI) use category

- This study does not collect or use any VASI
- This study uses but does not save, collect, copy, or record VASI
- This study does collect or record VASI

## Section 27.1 VA Sensitive Information (VASI)

### 27.1a) For each type of VASI, indicate all that apply:

Indicate which of the following will be collected/recorded:

- Protected Health Information (PHI)
- Names
- Device identifiers and serial numbers
- E-mail addresses
- Medical record numbers
- URLs (Universal Resource Locator)
- All elements of dates (except year) or any age over 89
- Health plan beneficiary numbers
- IP Addresses (Internet Protocol)
- Telephone numbers
- Account numbers
- Biometric Identifiers including finger and voice print
- Fax numbers
- Certificate or license numbers
- Full face photographic images and comparable images
- All geographic subdivisions smaller than a state
- Vehicle ID and serial numbers including license plate numbers
- Social security numbers or scrambled SSNs (describe below)
- Other unique identifying number, characteristic, or code (describe below)

27.1a1) Describe why SSN are needed for this study

SSN are needed for subject payment

**27.1b) Consent Forms and/or HIPAA Authorization**

Yes  No

**27.1c) Images with personal identifiers are used for this study (x-rays, MRI images with patient names, record numbers, dates, etc.)?**

Yes  No

**27.1d) Photos with faces or audio video recordings are used for this study.**

Yes  No

27.1d1) Identify the device or devices that will be used to take/make the photographs or recordings.

An audio recorder will be used to record group interventions to assess treatment fidelity. We will also be using a video-recorder to tape some of the intervention sessions for future training purposes. We will be using an Olympus 7000 Voice Recorder. We will be using a VA approved video camera to make video recordings.

27.1d2) Identify where images will be stored (e.g., in the medical record, with study hardcopy records, with study electronic VASI records

Audio recording will be transferred to a computer system and assigned group numbers, and will not be individually identifiable. The key relating group numbers to the individuals will be stored separately, protected by strong passwords, and accessible only by approved study personnel.

Video recordings will be uploaded to the VA secure network R drive (in R:\[name]) and will only be accessible to the approved study staff through PIV log in. The video recordings will also be on the video camera, in the PI's lab space, in a locked drawer in building #13, separate from the de-identified data files.

**27.1e) Biological specimens with identifiers are used for this study.**

Yes  No

**Section 27.2 Data Collection, Tools, and Resources**

**27.2a) Will any specially obtained software be used?**

Yes  No

**27.2b) Will any mobile devices (laptop, tablet, portable hard-drive, etc.) be used in support of this study?**

Yes  No

